7.3.2 Exclusion criteria

A subject who meets any of the following criteria is not eligible for participation in the study.

1. Known hypersensitivity or allergy to the active substance or excipients of Ferric maltol oral suspension or capsules;
2. Presence or history of any significant cardiovascular, gastrointestinal, hepatic, renal, pulmonary, hematologic, endocrine, immunologic, dermatologic, neurological, or psychiatric disease, as determined by the Investigator;
3. Presence or history of any other condition (including surgery) known to interfere with the absorption, distribution, metabolism, or excretion of medicines;
4. Recent (within 6 months of screening) history of drug or alcohol abuse;
5. Positive screen results for drugs of abuse, alcohol at screening or Study Day -1 of Period 1;

6. Consumption of alcohol within 72 hrs prior to study drug administration;
7. Positive test result for hepatitis B surface antigen (HBsAg), hepatitis C virus antibody (HCV Ab), or human immunodeficiency virus antibody (HIV Ab) at screening;
8. Donation or loss of 550 mL or more blood volume or receipt of a transfusions of any blood product within 8 weeks prior to study drug administration and 14 days for plasma donation unless medically inadvisable;
9. Use of any over the counter medications, including herbal product within 7 days prior to Screening until study completion. Except for ordinary pain (e.g. headache), some analgesics (mainly paracetamol) and contraception which have no drug interactions with the study products may be given;
10. Has received within 28 days prior to Screening intramuscular or intravenous (IV) injection or administration of depot iron preparation;
11. Has received oral iron supplementation within 7 days prior to Screening;
12. Has concomitant disease that would significantly compromise iron absorption or absorbed iron utilization such as swallowing disorders, gastric pH-disturbance and/or extensive small bowel resection;
13. Scheduled or expected hospitalization and/or surgery during the course of the study;
14. Diagnosed to be COVID-19 positive by polymerase chain reaction testing (SARS-CoV-2-RT-PCR positive) of a respiratory specimen (preferably a nasopharyngeal swab) on Day -2;
15. Participation in any other interventional clinical study within 28 days prior to Screening;
16. Any other unspecified reason that, in the opinion of the Investigator or the Sponsor makes the subject unsuitable for enrolment.

7.4 CONCOMITANT MEDICATION

7.4.1 Not Permitted

- Treatment with other oral iron preparations (prescription and non-prescription) within 7 days prior to screening and throughout the study period;
- Treatment with parenteral iron preparations within 28 days prior to screening and throughout the study period;
- Oral antibiotics, which are prohibited at screening and during the study;
- Blood transfusions within 12 weeks before screening and during the study;
- Erythropoiesis stimulating agents within 28 days before screening and during the study;
- Multivitamins within 7 days prior to screening and throughout the study period;
- Other prescription or over the counter medications, including herbal products from screening until study completion.

7.4.2 Permitted

- Oral contraceptives are allowed during the study, but the subjects must have been on a stable dose for 3 months before randomisation;
- If necessary, medication used for treatment of any emergent AE at the discretion of the Investigator may be given.

7.4.3 Potential Medication Interactions

Iron-drug interactions of clinical significance have been reported to occur with a large number of concomitant therapies. Concurrent ingestion of oral iron causes marked decrease in the bioavailability of a number of drugs due to the formation of iron-drug complexes (chelation or binding of iron by the second drug). Examples of affected drugs are: IV iron, penicillamine, bisphosphonates, ciprofloxacin, entacapone, levodopa, levofloxacin, levothyroxine (thyroxine) moxifloxacin, mycophenolate, norfloxacin, ofloxacin, tetracyclines, calcium and magnesium salts, dimercaprol, chloramphenicol and methyldopa.

To minimize the potential for drug interactions, concomitant medications should be taken at least 4 hrs after ferric maltol. The exact timing of any concomitant medication should be recorded in the eCRF.

7.5 INDIVIDUAL DISCONTINUATION CRITERIA

Subjects have the right to withdraw consent without prejudice at any time during the study. If a subject withdraws consent, the Investigator should make a reasonable effort to determine the cause. All withdrawn subjects should have a Post-Study Visit within 3-7 days at the Clinical Unit after the last dose of study drug (if the subject agrees in the case of withdrawn consent).

Subjects may be discontinued prematurely during the study for the following reasons:

- Withdrawal of informed consent
- Unwillingness or inability to comply with protocol requirements
- Pregnancy or not using a reliable method of birth control (female subject of childbearing potential)
- Use of prohibited concomitant medications
- Serious adverse events that are judged by the Investigator to be related to study treatment
- Blood transfusions for any cause during the study treatment period

The reason for study drug discontinuation and the date of last dose should be recorded in the eCRF. Subjects who discontinue treatment prematurely must return for the safety follow up

at the Clinical Unit 3-7 days after last medication, unless informed consent is withdrawn (and the subject do not agree to attend this visit follow-up visit).

7.6 STUDY TERMINATION

The Sponsor reserves the right to temporarily halt and/or terminate the study (or if appropriate, individual treatment dose groups) at any time for safety, scientific or ethical reasons including, but not limited to:

- Emerging safety concerns from this study, other ongoing studies with Ferric Maltol, or new and relevant scientific information, which result in the risk-benefit ratio for this study becoming unfavorable, in the Sponsor's opinion.
- If the total number of dropouts is so high or the number of included subjects is so low that completion of the trial will not realistically be expected within a reasonable timeframe.
- If the Sponsor determines the study will no longer reveal new knowledge and consequently is ethically no longer justifiable.

In case of an early termination of the study or temporary halt by the Sponsor, the IEC and CA will be notified within 15 calendar days, including a detailed written explanation of the reasons for the termination/halt.

In all circumstances connected with temporary halt and/or termination of the study, the following principles will apply:

- All affected parties (such as the IEC, CA, Investigators, heads of study center/clinic directors) must be informed as applicable according to local law.
- All study materials and supplies (except documentation that should remain stored at site) must be returned to the Sponsor/designee.

8 TREATMENT OF SUBJECTS

Healthy male and female subjects complying with the inclusion criteria and do not meet any of the exclusion criteria will be randomly assigned to 4 treatment sequence. 8 subjects will be randomized to each sequence:

Sequence A:

- *Period 1; single dose of 30 mg ferric maltol capsule in a fed condition*
- *Period 2; single dose of 30 mg (5 ml) ferric maltol suspension in a fed condition*
- *Period 3; single dose of 30 mg ferric maltol capsule in a fasted condition*
- *Period 4; single dose of 30 mg (5 ml) ferric maltol suspension in a fasted condition*

Sequence B:

- *Period 1; single dose of 30 mg (5 ml) ferric maltol suspension in a fasted condition*
- *Period 2; single dose of 30 mg ferric maltol capsule in a fed condition*
- *Period 3; single dose of 30 mg (5 ml) ferric maltol suspension in a fed condition*
- *Period 4; single dose of 30 mg ferric maltol capsule in a fasted condition*

Sequence C:

- *Period 1; single dose of 30 mg ferric maltol capsule in a fasted condition*
- *Period 2; single dose of 30 mg (5 ml) ferric maltol suspension in a fasted condition*
- *Period 3; single dose of 30 mg ferric maltol capsule in a fed condition*
- *Period 4; single dose of 30 mg (5 ml) ferric maltol suspension in a fed condition*

Sequence D:

- *Period 1; single dose of 30 mg (5 ml) ferric maltol suspension in a fed condition*
- *Period 2; single dose of 30 mg ferric maltol capsule in a fasted condition*
- *Period 3; single dose of 30 mg (5 ml) ferric maltol suspension in a fasted condition*
- *Period 4; single dose of 30 mg ferric maltol capsule in a fed condition*

8.1 INVESTIGATIONAL MEDICINAL PRODUCT (IMP) PRESENTATION

- 5 ml (6 mg/ml elemental iron) ferric maltol oral suspension.

A full list of excipients can be found in the Investigator's Brochure.

8.2 COMPARATOR

- 30 mg ferric maltol capsule

A full list of excipients can be found in the Investigator's Brochure.

8.3 TREATMENT ASSIGNMENT AND BLINDING

The randomization procedure (created using a computer-generated random permutation procedure) will randomize the subject to one of the 4 treatment sequences to either Sequence A Sequence B, Sequence C or Sequence D. The site will dispense the appropriate formulation of open-label ferric maltol bottles at each scheduled PK day according to the schedule of assessments.

This is an open label study and treatment assignment is not blinded.

8.3.1 TREATMENT ASSIGNMENT AND ADMINISTRATION

Ferric maltol capsule and suspension fasted conditions:

Prior to the first treatment period, subjects will arrive at the Clinical Unit on Day -1 at least 13 hrs before dosing. Eligibility will be checked again before randomization and subjects will be dosed after the 0 hrs baseline blood sample according to their randomized sequence. Capsules should be taken with 240 ml potable tap water, must be swallowed whole and must not be chewed, divided or crushed. 5 ml suspension will be measured out by using 2 x 3 ml syringe, graduated up to 2.5 ml. Subject can take suspension with 240 ml potable tap water if needed.

A hand and mouth check will be performed immediately after drug administration to ensure that the study drug has been swallowed.

Water is allowed during the 10 hrs fasting but not allowed for 1 hr before and 2 hrs post-dose (except for drug administration). No food will also be allowed for at least 4 hours post-dose. Within 30 mins following the 4 hours post-dose blood samples, subjects will receive a standardized meal.

Blood samples will be taken at 11 additional times after dosing; post-dose PK sample times will be 15 mins \pm 2 min, 30 mins \pm 2 min, 45 mins \pm 5 min, 1 hr \pm 5 min, 1,5 hr \pm 5 min, 2 hrs \pm 5 min, 3 hrs \pm 5 min, 4 hrs \pm 5 min. 6 hrs \pm 10 min, 10 hrs \pm 15 min and 24 hrs \pm 15 min.

Standard meals will be provided to the subjects at 4, 8, 12 hrs after drug administration in the morning. Meals will be identical in each treatment period. Iron content and time of consumption of each meal will be recorded during the hospitalization in the eCRF.

Subjects will have the following mealtimes:

- Lunch will be served: approximately 4 hrs post-dose
- Snack will be served: approximately 8 hrs post-dose

- Dinner will be served: approximately 12 hrs post-dose

Subjects will stay in the Clinical Unit throughout the study period. During the washout, subjects will stay at the Clinical Unit and receive standard meals. Iron content of the meals will be measured and recorded in the eCRF.

Ferric maltol capsule and suspension fed conditions:

Prior to the first treatment period, subjects will arrive at the Clinical Unit on Day -1 at least 13 hrs before dosing. Eligibility will be checked again before randomization. Subjects will then have their baseline blood samples taken and receive a test meal 30 minutes prior to administration of ferric maltol. Subjects should finish their meal in 30 minutes or less; however, ferric maltol will be administered 30 minutes after start of the meal. Capsules should be taken with 240 ml potable tap water. Suspension can be taken with 240 ml potable tap water if needed.

A hand and mouth check will be performed immediately after drug administration to ensure that the study drug has been swallowed.

Water is allowed during the 10 hrs fasting but not allowed for 1 hr before and 2 hrs post-dose (except for drug administration). No food will also be allowed for at least 4 hours post-dose. Within 30 mins following the 4 hours post-dose blood samples, subjects will receive a standardized meal.

Blood samples will be taken at 11 additional times after dosing; the post-dose PK sample times will be 15 mins \pm 2 min, 30 mins \pm 2 min, 45 mins \pm 5 min, 1 hr \pm 5 min, 1,5 hr \pm 5 min, 2 hrs \pm 5 min, 3 hrs \pm 5 min, 4 hrs \pm 5 min, 6 hr \pm 10 min, 10 hrs \pm 15 min and 24 hrs \pm 15 min.

Standard meals will be provided to the subjects at 4, 8, 12 hrs after drug administration in the morning. Meals will be identical in each treatment period. Iron content and time of consumption of each meal will be recorded during the hospitalization.

Subjects will have the following meal times:

- Breakfast will be served 30 minutes prior to drug administration
- Lunch will be served: approximately 4 hrs post-dose
- Snack will be served: approximately 8 hrs post-dose
- Dinner will be served: approximately 12 hrs post-dose

A test meal should consist of, 150, 250, and 500-600 calories protein, carbohydrate and fat respectively. An example meal: 2 eggs fried in butter, 2 strips of bacon, 2 slices of toast with butter, 4 ounces (113 g) of hash brown, potato and 8 ounces (227 ml) of water. Substitutions in this test meal can be made as long as the meal provides a similar amount of calories from protein, carbohydrate, and fat and has comparable meal volume and viscosity. If the meal is different from the above mention, it should be documented in the eCRF.

Subjects will stay in the Clinical Unit throughout the study period. During the washout, subjects will stay at the Clinical Unit and receive standard meals. Iron content of the meals will be measured and recorded in the eCRF.

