12 STATISTICAL CONSIDERATIONS

12.1 SAMPLE SIZE AND POWER CALCULATIONS

The sample size is based on the comparisons of each of the primary PK parameters C_{max} and AUC_{last} for total serum iron between the formulations, within each of the two conditions: fed and fasted. Each comparison will be made via the ratio of the two values of the parameter between the formulations. The 90% confidence interval (CI) for this ratio will be reported.

For each of the two comparisons (suspension vs capsule (fed condition); suspension vs capsule (fasted condition)) the CIs for two parameter ratios (C_{max} and AUC_{last}) for serum iron will be calculated, making a total of 4 CIs. If these ratios were all independent, and the probability of being within (80%, 125%) was 80% for each, then the probability that all 4 would fall within the required limits would be $(80\%)^4 = 41\%$. With individual probabilities of 90%, the combined probability would be 66%. However, if the ratios were positively correlated, the combined probabilities would be higher.

Data from a previous study (ST10-01-101) were used to provide estimates of the standard deviations (SDs) of the logs of the within-subject ratios of the parameters C_{max} and AUC_{last} , for both total serum iron and TSAT. Assuming the SD is no greater than 0.38, if the true ratio is 1, 31 subjects would provide a probability of at least 80% of all 4 CIs lying within (80%, 125%).

The aim of the study is to demonstrate that the 4 CIs for serum iron are all within (80%, 125%). As the SD, and the degree of correlation, are uncertain, 32 subjects will be recruited to the study.

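### Capsules are directed to be taken with 240 ml of water but water with the suspension is optional, so the suspension/capsule ratios, chiefly the two fasted ones, may mix formulation with dosing water

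*Protocol*

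**What the plan says.** For the fasted condition, Protocol 8.3.1 states for the capsule: "Capsules should be taken with 240 ml potable tap water, must be swallowed whole and must not be chewed, divided or crushed". The suspension sentence in the same paragraph is permissive: "Subject can take suspension with 240 ml potable tap water if needed". The fed part repeats it: "Suspension can be taken with 240 ml potable tap water if needed". The Administration entry of the Synopsis and footnote 12 of Section 10.2 use the same rule for both conditions, so this is not a slip in one place.

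Other water is barred from 1 hour before to 2 hours after dosing. The water taken with the dose is the exception.

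Other intake is controlled closely. Meals are identical across periods, and for these "Iron content and time of consumption of each meal will be recorded during the hospitalization in the eCRF". Substitutes for the test meal must match it in volume and viscosity, and a departure is documented.

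On the comparison itself, Protocol 12.1 says: "Each comparison will be made via the ratio of the two values of the parameter between the formulations". Its stated aim is that all four 90% CIs (Cmax and AUClast of total serum iron, fed and fasted) lie within 80-125%.

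**The concern.** A crossover removes differences between subjects and, with balanced sequences, differences between periods. It cannot remove a condition that switches whenever the formulation switches, and the dosing-water rule does that. If water taken with the dose affects iron absorption, the effect enters the suspension/capsule ratio and is reported as a formulation effect.

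Protocol 5.5 wants the trial to confirm that the two products are therapeutically interchangeable, and Protocol 8.8 sends the results to the FDA before the pediatric Phase III study. A CI outside the limits could then be due to formulation, to water or to both. A CI inside them could rest on two effects that offset. If the water taken is not recorded, the reader cannot judge which.

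**Working it through.** **1. The instructions side by side.** A suspension dose is 5 ml. The text offers 240 ml of water or none. The fed column assumes the example meal in 8.3.1, with 227 ml of water, begun 30 minutes before dosing.

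| Fluid around the dose | Fasted | Fed, example meal |
|---|---|---|
| Capsule | 240 ml | 227 + 240 = 467 ml |
| Suspension, water taken | 5 + 240 = 245 ml | 227 + 245 = 472 ml |
| Suspension, no water | 5 ml | 227 + 5 = 232 ml |

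If no water is taken, the gap is 235 ml in both conditions. Relative to what is already in the stomach it is far smaller after the meal, so the fasted ratios carry most of the concern. These are fluid volumes and say nothing direct about exposure. (The fed text also repeats the one-hour water ban, which sits awkwardly with water in that meal. The two statements should be reconciled.)

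**2. Can the design or the model separate water from formulation?** Every subject takes capsule twice and suspension twice, so sequence does not balance the water rule. The model in SAP 3.5.5 has sequence, treatment and period as fixed effects and subject within sequence as random. It has no term for water, so an average water effect falls into the treatment contrast, and variation in water use among suspension doses falls into the residual.

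**3. The plan's own sample size.** Inputs from Protocol 12.1 and SAP 2.2.4 are SD of the log ratio 0.38, true ratio 1, limit ln 1.25 = 0.2231, and 90% CI (5% per bound). Counting one limit only, n = [SD × (z0.95 + z_power) / ln 1.25]².

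- One CI, power 0.80: [0.38 × (1.645 + 0.842) / 0.2231]² = 17.9. The noncentral t version gives the stated 20.
- Four independent CIs, power 0.80^(1/4) = 0.946 each: [0.38 × (1.645 + 1.605) / 0.2231]² = 30.6, the stated 31.

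The stated figures are thus reproduced when one limit is counted. With both limits the power per CI at n = 32 is 0.891, the baseline below. That gap is a separate matter and does not affect this point.

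**4. What a shift of a given size would do.** The shifts are assumptions. At n = 32 the standard error is 0.38 / √32 = 0.0672 and t(0.95; 31) = 1.696. The half-width at the expected SD is 1.696 × 0.0672 = 0.1139, so the observed mean log ratio must lie within ±(0.2231 − 0.1139) = ±0.1092.

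- Ratio 1: 0.1092 / 0.0672 = 1.63, probability about 0.90.
- Ratio 0.95 (ln = −0.0513): from (−0.1092 + 0.0513) / 0.0672 = −0.86 to (0.1092 + 0.0513) / 0.0672 = 2.39, about 0.80.
- Ratio 0.90 (ln = −0.1054): from −0.06 to 3.19, about 0.52.

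Averaging over the chi-square distribution of the estimated variance gives the exact values:

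| True ratio | SD 0.38 | SD 0.30 |
|---|---|---|
| 1 | 0.891 | 0.986 |
| 0.95 | 0.795 | 0.936 |
| 0.90 | 0.527 | 0.701 |

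Upward shifts act similarly: at SD 0.38, ratios of 1.05 and 1.10 give 0.804 and 0.584.

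**5. Mixed use of water.** Suppose half of the suspension doses are taken without water and that multiplies exposure by 0.90. The mean ratio is exp(0.5 × ln 0.90) = 0.949, the SD is √(0.38² + 0.25 × 0.1054²) = 0.384, and the probability is 0.78. The full 0.53 would need the whole shift to apply to every suspension dose.

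**The case against.** The best defense is that the difference may be intended. A capsule needs water to be swallowed and 5 ml of liquid may not, so comparing each product as it would be taken is a legitimate question. That stands, but the text does not ask that question either. It fixes neither water nor no water for the suspension, so the contrast is left undefined.

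Second, the size is unknown. The primary endpoint is total serum iron, so endogenous iron is in both numerator and denominator. If a share a of measured exposure comes from the dose, a change of x% in absorbed iron moves the ratio by only a × x%. A 5% shift in the primary ratio therefore needs a larger change in absorption. This stands, and the figures above must be read as net shifts of the primary ratio.

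Third, details may lie elsewhere. Protocol Section 9 refers full procedures to the Investigator Site File and the eCRF Completion Guidelines. A reader might infer that the volume is not captured and that later adjustment is impossible. The documents are only silent on this.

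A reader might also infer two further things that the documents do not support:

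- **Cmax is affected most**, because six of the eleven post-dose samples fall within the 2-hour water ban. The ban applies to both formulations and no iron Tmax is given.
- **Suspension left in the syringes or mouth underdoses that arm.** At 6 mg/ml, 0.1 ml is 0.6 mg, or 2% of 30 mg. But drinking water does not empty a syringe, a hand and mouth check follows each dose, and the pediatric study in Protocol 5.4.3 found iron exposure less than dose proportional, with a plateau between 16.6 and 30 mg on Day 1. It is a separate and weak point.

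**Conclusion.** The point holds as an avoidable weakness of the design. Dosing water is tied to formulation, may vary among suspension doses, and is not stated to be recorded, so the suspension/capsule ratios may mix the two. The two fasted ratios are the main concern. The fed ratios share the wording, but the example meal reduces the relative difference.

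It does not follow that the ratios are biased. The wording permits variation without showing that it will occur; if every suspension dose were taken with 240 ml there would be almost no difference. Nor is the choice said to be the subject's own, since staff give each dose.

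The only quantification is conditional: at n = 32 and SD 0.38, a net shift from 1 to 0.95 or 0.90 takes the per-CI probability from 0.891 to 0.795 or 0.527. It rests on normal paired log ratios, the protocol's upper SD and assumed shifts. A zero effect leaves 0.891 unchanged, and a shift could equally mask a real difference of similar size.

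**What to change.** Reconcile the dosing-water instructions in Protocol 8.3.1 (fasted and fed), the Synopsis and footnote 12 of Section 10.2, so that one fixed instruction applies to both formulations in all four periods. The sponsor should choose it; this review does not. Record the volume actually taken with each dose in the eCRF.

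If the sponsor means to test the suspension without water, state that and fix it for every suspension dose. The ratio is then a defined comparison of each product with its own dosing instruction.

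The cost is a short amendment in three places and one eCRF field, in an inpatient study where staff administer every dose. The small downside is that the suspension is tested under only one water condition.
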